#### **Secondary efficacy endpoints:**

To evaluate the safety and tolerability of two oral formulations of enzalutamide following a single 160 mg dose in male subjects with prostate cancer.

### **8.2 SAMPLE SIZE DETERMINATION**

This study will be conducted as a two-period randomized crossover trial design. Patients will be randomized to initially receive the standard liquid filled soft gelatin formulation (Arm A) followed later by the liquid formulation, or the liquid formulation as the test product (Arm B)

Abbreviated Title: Enzalutamide Formulation PK  
Version Date: 03.11.2020

followed by the liquid filled soft gelatin formulation. A total of 12 evaluable patients will be randomized into the two arms. It has been identified that a decrease of approximately 30-40 ug\*h/mL in the AUC (less than a 20% decrease in the AUC for the test version vs. the standard formulation) would permit the two formulations to be considered bioequivalent, and it may be expected that the actual difference between the formulations may be a decline of approximately 10% (approximately 20 ug\*h/mL). When the sample size in each sequence arm is 6, (a total sample size of 12) a crossover design will have 80% power to reject the null hypothesis that the Arm B mean minus the Arm A mean is below -40 ug\*h/mL and the null hypothesis that the Arm B mean minus the Arm A mean is above 0 ug\*h/mL, i.e., that the two groups are not equivalent, in favor of the alternative hypothesis that the means of the two treatments are equivalent, assuming that the expected difference in means is -20 ug\*h/mL, the standard deviation of differences,  $s_d$ , is 20 ug\*h/mL, and that each test is made at the 5% level.

It is expected that approximately 1 patient per month may enroll onto this trial. Thus, to enroll 12 evaluable patients, it is anticipated that one year may be required. To allow for the possibility of a small number of patients who do not have full measurements obtained based on both drug administrations, the accrual ceiling will be set at 14 patients.

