#### **1.2.2 Pharmacokinetic Studies**

Multiple clinical pharmacokinetic studies of enzalutamide have been conducted [7]. Enzalutamide has a half-life of 5.8 days, achieves steady state by day 28, accumulates 8.3-fold with once-daily dosing, shows approximate dose proportionality from 30–360 mg/day, and has <30 % intersubject variability. It is primarily eliminated by hepatic metabolism, while renal excretion is an insignificant elimination pathway for enzalutamide and its active metabolite, N – desmethyl enzalutamide. Exposure to enzalutamide active moieties is not affected by food or baseline mild or moderate hepatic impairment. Enzalutamide has predictable pharmacokinetics, with low intersubject variability. Similar efficacy was observed in patients across the concentration/exposure range associated with a fixed oral dose of enzalutamide 160 mg/day.

*Abbreviated Title: Enzalutamide Formulation PK*  
*Version Date: 03.11.2020*

Study NCT01911715 was a phase I, open-label, one-period, single-dose mass balance and biotransformation study in six healthy male subjects [7]. After a single oral dose of enzalutamide 160 mg (4 x 40 mg capsules), at least 84.2% of the drug was absorbed. The average  $C_{max}$ ,  $t_{max}$ ,  $AUC_{inf}$ , and  $t_{1/2}$  of enzalutamide were 4.5 ug/mL, 1.8 h, 237 ug\*h/mL, and 2.9 days, respectively.

A phase I, open-label, randomized, single-dose, parallel design, food-effect study was performed in 60 healthy men (n=30 in fasted and fed arms) to determine the effect of a high-fat meal on the pharmacokinetics of enzalutamide [7]. The average  $C_{max}$  and  $T_{max}$  for the fasted and fed arms were 5.3 and 3.7 ug/mL and 1 and 2h post-dose, respectively. The average  $AUC_{inf}$  for the fasted and fed arms were 292 and 285 ug\*h/mL, respectively. In all, the data suggest that consumption of a high-fat meal slightly slows the rate of absorption but does not lower exposure of enzalutamide.

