Gibbons et al. conducted two phase I drug interaction studies: one investigating the effects of coadministered drugs on the pharmacokinetics of enzalutamide, and one investigating the effects of enzalutamide on the pharmacokinetics of coadministered drugs [8]. Study NCT01913379, which used a parallel-treatment design (n=41), studied the effects of a strong CYP2C8 inhibitor (p.o. gemfibrozil 600 mg twice daily) and a strong CYP3A4 inhibitor (p.o. itraconazole 200 mg once daily) on the pharmacokinetics of enzalutamide after a single dose of enzalutamide (160 mg). Coadministration of gemfibrozil and itraconazole increased the  $AUC_{inf}$  of enzalutamide by 2.2- and 1.3-fold, respectively. Study NCT01911728, which used a single-sequence cross-over design (n=14), studied the effects of enzalutamide (160 mg/day) on the pharmacokinetics of a single oral dose of sensitive substrates for CYP2C8 (picoglitazone 30 mg), CYP2C9 (warfarin 10 mg), CYP2C19 (omeprazole 20 mg), or CYP3A4 (midazolam 2 mg). The  $AUC_{inf}$  of warfarin, omeprazole, and midazolam were decreased by 56, 70, and 86%, respectively, after coadministration of enzalutamide, suggesting that enzalutamide is a moderate inducer of CYP2C9 and CYP2C19 and a strong inducer of CYP3A4.

A randomized, two-period crossover pilot bioequivalence and food effect study was carried out in 60 healthy male subjects to compare two enzalutamide formulations [9]. The reference formulation, which had previously been used in human clinical trials, was a liquid-filled soft gelatin capsule containing 40 mg enzalutamide dissolved in Laprasol. Four capsules were necessary to deliver 160 mg enzalutamide. The test formulation was a tablet composed of 160 mg enzalutamide in a 60%A:hydroxypropyl methylcellulose acetate succinate (HPMCAS)-M spray dried dispersion. While cohorts A and B (n=15, each) were fasted, cohorts C and D (n=15, each) were fed. Cohorts A and C were given a single dose of 160 mg enzalutamide as a tablet. Cohorts B and D were given a single dose of 160 mg enzalutamide as 4x40 mg liquid-filled capsules. After a 42-day washout, cohorts A and B, C and D were crossed over. The average  $AUC_{day1-7}$  for the tablet and capsule formulations in fasted subjects was 177 and 185 ug\*h/mL, respectively. The average  $AUC_{day1-7}$  for the tablet and capsule formulations was 191 and 187 ug\*h/mL, respectively. In all, the data suggest that the bioequivalence of the formulations was comparable.

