## **8 STATISTICAL CONSIDERATIONS**

### **8.1 STATISTICAL HYPOTHESES**

#### **Primary efficacy endpoints:**

To evaluate the bioequivalence of two oral formulations of enzalutamide following a single 160 mg dose in male subjects with prostate cancer.

The primary measure of efficacy will be AUC for the first period of administration obtained during blood draws during visits on day 1, 3, 8, and 42 evaluations, and then AUC at a second set of visits at least 42 days after the first administration, for evaluations on days 1, 3, 8 and 42 relative to the second administration, for the second period evaluations.

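### The 40 ug·h/mL limit and the 20 ug·h/mL expected difference in 8.2 imply a reference AUC near 200; if the primary AUC runs to Day 42, the protocol's own figures put it near 237-292, so both are mis-scaled

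*Combined protocol and SAP*

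**What the plan says.** Section 8.2 describes the acceptable loss of exposure, relative to the capsule, in absolute and relative terms: "a decrease of approximately 30-40 ug\*h/mL in the AUC (less than a 20% decrease in the AUC for the test version". It then says that "the actual difference between the formulations may be a decline of approximately 10% (approximately 20 ug" (the unit is cut short here; AUC is in ug·h/mL). The planning test has two one-sided nulls. The lower one is "the null hypothesis that the Arm B mean minus the Arm A mean is below -40 ug" (same unit), and the upper one puts this difference higher than zero. The plan assumes a true difference of -20, an SD of differences of 20, 5% per test, 6 men per sequence and 80% power. Section 8.2 does not say which AUC these figures refer to or where the SD comes from.

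Section 8.1 defines the primary measure as "AUC for the first period of administration obtained during blood draws during visits on day 1, 3, 8, and 42 evaluations", with the same set of draws after the second dose. Section 5.1 collects samples over 42 days because of the long half-lives. Section 8.4.2 analyses an average of AUC values over four determinations per administration and gives no end of integration.

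Section 1.2.2 holds the only AUC figures, all in ug·h/mL. In the earlier tablet-capsule crossover, the AUC over days 1-7 "for the tablet and capsule formulations in fasted subjects was 177 and 185"; the second pair, by context the fed cohorts, has 187 for the capsule. The AUC to infinity is 237 in the mass balance study (160 mg as capsules), and in the food-effect study the averages "for the fasted and fed arms were 292 and 285".

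**The concern.** An absolute limit has a relative meaning only once the reference AUC is known. The 10%/20 pair in 8.2 fixes that reference near 200. The only capsule AUCs close to 200 are 7-day values, whereas 8.1 and 5.1 point to a 42-day measurement, for which the protocol's own figures are larger. If limit and measurement are on different scales, a liquid with exactly the 10% decline that 8.2 expects sits closer to the lower limit than planned. The trial could then miss equivalence for a product that the planners meant to accept. With an accrual ceiling of 14, there is little room to recover lost power.

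**Working it through.** **Inputs.** From 8.2: limits -40 and 0, expected difference -20 (called about 10%), SD of differences 20, one-sided 5% per test, N = 12. From 1.2.2: capsule AUC over days 1-7 of 185 and 187; AUC to infinity of 237, 285 (fed) and 292 (fasted); half-life 5.8 days (2.9 in the mass balance study).

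**1. Reproduce the plan's figure.** For a two-period crossover, SE = SD/√N = 20/√12 = 5.77 with N - 2 = 10 degrees of freedom, and the one-sided 5% t value is 1.812. Equivalence is declared when estimate - 1.812 × SE exceeds -40 and estimate + 1.812 × SE is below 0, with SE estimated from the data. Exact joint power, integrating over the sample SD, is 78.4% at N = 10 and 88.4% at N = 12. So 12 is the smallest balanced size that reaches 80%, and the plan's number reproduces.

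**2. Reference AUC implied by 8.2.** 20/0.10 = 200 ug·h/mL, so the limit is 40/200 = 20%.

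**3. Share of the AUC reached by Day 42.** For a terminal phase with half-life 5.8 days: 1 - 2^(-42/5.8) = 99.3%. With 2.9 days it is above 99.9%. A 0 to Day 42 AUC is therefore close to the AUC to infinity.

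**4. The figures of 8.2 on each scale.**

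| Reference AUC (ug·h/mL) | 20 is | 30 is | 40 is | 10% is | 20% is |
|---|---|---|---|---|---|
| 185 (days 1-7, fasted) | 10.8% | 16.2% | 21.6% | 18.5 | 37.0 |
| 200 (implied by 8.2) | 10.0% | 15.0% | 20.0% | 20.0 | 40.0 |
| 237 (to infinity, mass balance) | 8.4% | 12.7% | 16.9% | 23.7 | 47.4 |
| 292 (to infinity, fasted) | 6.8% | 10.3% | 13.7% | 29.2 | 58.4 |

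**5. Joint power at N = 12 with a true 10% decline and limits kept at -40 and 0.** The SD is either held at 20 or set to 10% of the AUC, the ratio it has to the implied 200.

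| Reference AUC | True difference | SD = 20 | SD = 10% of AUC |
|---|---|---|---|
| 200 | -20.0 | 88% | 88% (SD 20) |
| 237 | -23.7 | 82% | 66% (SD 23.7) |
| 292 | -29.2 | 54% | 27% (SD 29.2) |

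**6. All three inputs rescaled together.** With limits of -20% and 0, difference -10% and SD 10% of the AUC, the distance from the expected difference to either limit is again one SD. Power stays at 88% for any reference AUC.

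**The case against.** The case against has several parts, and much of it stands.

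- A reader might infer that the limit contradicts a stated 20%. It does not. Section 8.2 says "less than a 20% decrease in the AUC for the test version vs. the standard formulation", and 30-40 is 10.3-16.9% of 237-292, which satisfies that wording. The tension lies in the 10%/20 pair alone. At 237, where 20 is 8.4%, it is mild; at 285-292, where 20 is about 7%, it is clear.
- A reader might infer that 8.2 took its figures from the 7-day AUC. That is plausible but unproven: the implied reference is 200, not 185-187, and 8.2 names no source or window. The mismatch with a 42-day AUC does not depend on the origin.
- The end of integration is not settled. Section 8.1 lists visit days, and 8.4.2 averages four determinations. If those were cumulative AUCs to 24 h, 48 h, 168 h and Day 42, a one-compartment sketch (my assumption: AUC × (1 - 2^(-t/half-life)), AUC to infinity 237-292, half-life 2.9-5.8 days) gives an average of about 112-176. Then 40 would be about 23-36%, looser than 20%. So the 14-17% figure is conditional on an AUC to Day 42.
- A reader might infer that the trial will be decided against -40. Sections 8.4.1 and 8.4.2 assess the difference at the 0.05 level by a non-parametric method and never mention the limit. The power figures above belong to the planning test in 8.2.
- At 237 with SD 20, power is 82%, still above the 80% claimed.
- A tighter limit raises the risk of missing equivalence, not of declaring it falsely. The protocol also calls this a pilot study (1.2.4, 3.1), and section 10 says it is not meant to support a significant labelling change.

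These points reduce the certainty and the harm. None of them says which AUC the limit refers to, and no section does.

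**Conclusion.** The point holds conditionally. If the primary AUC runs to Day 42, as the draws in 8.1 and 5.1 suggest, the 40 ug·h/mL limit is about 14-17% of the reference instead of the 20% implied by 8.2, and its expected 10% decline is about 24-29 ug·h/mL instead of 20. Joint power then falls from 88% to between 82% and 54% with SD 20, or between 66% and 27% with the SD at 10% of the AUC.

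This rests on three assumptions. First, AUCs to infinity from healthy men stand in for a 42-day AUC in patients. Second, the food-effect averages refer to a 160 mg dose, which the summary in 1.2.2 does not state. Third, the SD lies within the two cases shown, since the documents give none for this window.

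The result does not show that 12 is miscalculated: it follows from its own inputs, and it is the scale of those inputs that is in doubt. The point is also separate from the choice of zero as the upper limit, which is left as planned here. It should be fixed, with moderate confidence.

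**What to change.** In 8.1 and 8.4.2, define one AUC interval per administration, for example 0 to Day 42 to match the sampling, in place of the average over four determinations. State the integration rule as well, since no draw falls between Day 8 and Day 42. In 8.2, restate the limit as 20% of the reference mean on that interval (about 47-58 ug·h/mL for a 42-day AUC) or as a test/reference ratio. Give the 10% expected difference (about 24-29 ug·h/mL) and the SD on the same scale, with the source of the SD. Because 8.3 keeps men with draws on three of the four dates, say how the AUC is obtained when the draw that closes the interval is missing.

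Switching to a 0-168 h AUC while keeping the 40 limit is not a clean alternative: 40 is 21.6% of 185, which breaks the under-20% wording in 8.2, and the Day 42 draw would no longer contribute to the primary measure.

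The cost is wording, with no change to visits, samples or, if all three inputs scale together, the 12 men. The downside is that the planning difference and SD must be restated, and the SD on the larger scale remains an assumption.

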#### Arms

Letter	Name	Description
A	Sequence AB	Enzalutamide capsule (Treatment A) followed by enzalutamide liquid (Treatment B)
B	Sequence BA	Enzalutamide liquid (Treatment B) followed by enzalutamide capsule (Treatment A)

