### 8.4 STATISTICAL ANALYSES

#### 8.4.1 General Approach

The difference in the AUCs will be calculated following a published non-parametric approach for analyzing data from two-period cross-over studies:

Koch GG "The Use of Non-parametric methods in the statistical analysis of the two-period change-over design. *Biometrics* 28: 577-584 (1972).

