#### 8.4.2 Analysis of the Primary Efficacy Endpoints

The average of the AUC values at the 4 determinations associated with each of the two drug administrations will be determined and the difference assessed for statistical significance at the 0.05 level using the non-parametric procedures identified in the Koch 1972 paper.

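### Section 8.2 powers two one-sided equivalence tests, but 8.4.2 runs only a test of difference, which cannot show bioequivalence

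*Combined protocol and SAP*

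**What the plan says.** The primary objective (1.1.1, repeated in 8.1) is to evaluate the bioequivalence of the liquid and the capsule.

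Section 8.2 sets up two one-sided tests, each at 5%. It says that "a crossover design will have 80% power to reject the null hypothesis that the Arm B mean minus the Arm A mean is below" a lower limit of -40 ug*h/mL, and the other test is of "the null hypothesis that the Arm B mean minus the Arm A mean is above 0" ug*h/mL. Rejecting both means equivalence. The assumptions are a true difference of -20, an SD of differences of 20 and 6 patients per sequence. The stated power is 80%.

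The analysis sections describe something else. Section 8.4.1 names "a published non-parametric approach for analyzing data from two-period cross-over studies" and cites a 1972 methods paper. Section 8.4.2 averages the AUC values for each administration and has "the difference assessed for statistical significance at the 0.05 level using the non-parametric procedures" of that paper. Neither section mentions -40, 0, one-sided tests, a confidence interval or the word equivalence.

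The arms table in 2.3.1 defines Arm A as sequence AB and Arm B as sequence BA, so every patient in either arm receives both formulations.

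**The concern.** A test of difference and a test of equivalence answer different questions. Failing to find a difference in 12 patients does not show that the formulations are close. Finding one does not show that they differ by more than the margin. As written, 8.4 contains no rule by which the trial could reach a conclusion on its primary objective, and the power that justifies N = 12 belongs to tests that the plan does not perform.

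Two smaller matters sit in the same paragraph of 8.2. The 80% is not the power that the printed inputs give. The hypotheses, read literally, contrast two sequences rather than two formulations.

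**Working it through.** **Inputs, all from 8.2:** limits -40 and 0; expected difference -20; SD of differences 20; N = 12 (6 per sequence); 5% for each one-sided test. All AUC figures are in ug*h/mL.

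**1. The plan's own power figure.**
- Standard error = 20/√12 = 5.774. Degrees of freedom = 12 - 2 = 10. One-sided 5% critical value t = 1.812.
- Equivalence is concluded if (estimate - 1.812 × SE) > -40 and (estimate + 1.812 × SE) < 0.
- The true value lies 20 from each limit, so each test has noncentrality 20/5.774 = 3.464 and power 94.2%.
- Both tests together: the noncentral t gives 88.4%, and integrating over the distribution of the variance gives the same. As a check, 1 - 2 × (1 - 0.942) = 0.884.
- With 5 per sequence (N = 10) the power is 78.4%. Six per sequence is therefore the smallest balanced design that reaches 80%.

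The stated 80% is not the power at N = 12, but as a target it leads exactly to N = 12.

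**2. What the 8.4.2 test does in the same scenario.** The true difference is -20, which 8.2 treats as equivalent.
- Two-sided t test at 0.05: noncentrality -3.464, 10 degrees of freedom, significant in 87.6% of trials.
- Rank-based form. The plan does not say which procedure of the cited paper applies. I assume an exact rank-sum test of within-patient period differences, 6 against 6, with normal data. The attained two-sided level is 2 × 2.06% = 4.1%. In 20,000 simulated trials it was significant in 82.9%.

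**3. The two rules applied to one result.**
- Suppose the trial observes exactly what was planned: estimate -20, SD 20. Then t = -20/5.774 = -3.46, beyond the two-sided 5% value of 2.228, so 8.4.2 reports a significant difference. The 90% interval is -20 ± 1.812 × 5.774 = -30.5 to -9.5. It lies inside -40 to 0, so 8.2 concludes equivalence.
- Now double the SD to 40, as an illustration. SE = 40/√12 = 11.547 and t = -1.73, which is not significant under 8.4.2. The 90% interval is -20 ± 20.9 = -40.9 to 0.9. It crosses both limits, so 8.2 does not conclude equivalence.

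The two rules point in opposite directions in both cases.

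**4. The upper limit of 0.** Rejecting a difference above 0 requires the liquid to be lower than the capsule at one-sided 5%. If the formulations are identical, the true difference lies on that limit, and the 8.2 procedure declares equivalence in only 5.0% of trials (4.5% in the assumed rank form). Section 1.2.4 says the liquid is drawn from the capsule itself, so a true difference near zero is not far-fetched. For comparison only, limits of -40 and +40 at N = 12 would give 94.2% power at -20 and more than 99.9% at 0.

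**The case against.** **The 80% is a design target.** This is a fair reading, and it stands. Whole patients and balanced sequences move the achieved power from 78.4% to 88.4%, and all that is missing is *at least*. The discrepancy is in the safe direction and N does not change.

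A reader might go further and infer that an input is misprinted, since an SD of 22 would give 80.0% and a lower limit of -37 (20% of the capsule AUC of 185 in 1.2.2) would give 80.5%. The documents do not support this. Both values are found only by working back from 80%, neither is printed as an input, and rounding up to a balanced design explains the gap. A reader might also take 20 as a root mean square error, giving 48% power. But 8.2 explicitly labels it the standard deviation of differences.

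**The arm wording is only a label.** This largely stands. Section 8.2 attaches Arm A to the capsule and Arm B to the liquid, and it words the alternative in terms of the two treatments. The intended contrast is clear, although the label conflicts with 2.3.1.

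**The rank figures depend on an assumed procedure.** This stands too. The 83% is indicative. The t-test figure of 88% needs no such choice, but it is not the non-parametric method that 8.4 names.

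**The intent is equivalence, so the analyst would apply the 8.2 limits anyway.** The intent is plain from 1.1.1 and 8.2. But 8.4 states the analysis explicitly and nothing elsewhere in the document ties it to limits. Choosing a decision rule after the data are seen would not be prespecified.

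**Conclusion.** The mismatch between 8.2 and 8.4.2 is real and material. Followed as written, the plan cannot establish its primary objective. In its own planning scenario it would report a significant difference in about 88% of trials (t test) or about 83% (assumed rank-sum form, normal data). If a non-significant result were instead taken as equivalence, a reading that the plan does not state, the trial would succeed in only about 12% (100 - 87.6) or 17% (100 - 82.9) of trials in that scenario.

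Copying the 8.2 limits into 8.4.2 would not be a complete repair, because the upper limit of 0 passes identical formulations only 5% of the time.

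The power figure and the arm label are minor wording points. The sample size of 12 follows from the printed inputs. These conclusions rest on the inputs in 8.2 as printed and on approximately normal differences.

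**What to change.** 1. In 8.4.2, replace the significance test with a decision rule: conclude equivalence if the 90% confidence interval for liquid minus capsule lies wholly within prespecified limits (two one-sided tests at 5% each). State whether the interval is t-based or rank-based. If it is rank-based, name the exact procedure.
2. Before carrying the 8.2 limits over, reconcile the upper limit of 0 with the aim of showing that the formulations are equivalent. State the limits finally chosen with their reason, and restate the power for those limits and that method.
3. In 8.2, if the printed limits are kept with t-based tests, write that 6 per sequence gives at least 80% power (88% at N = 12; 5 per sequence gives 78%). If rank-based tests are chosen, compute the power for the named procedure; the form assumed here gives about 84%.
4. In 8.2, write both hypotheses as Treatment B (liquid) minus Treatment A (capsule).

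The cost is wording in 8.2 and 8.4.2 and one decision on the limits, all to be settled before the data are analyzed. At the printed inputs no extra patients, samples or visits are needed.

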## **1 INTRODUCTION**

### **1.1 STUDY OBJECTIVES**

#### **1.1.1 Primary Objective**

- To evaluate the bioequivalence of two oral formulations of enzalutamide following a single 160 mg dose in male subjects with prostate cancer

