#### 10.1.4 Stability and Storage

Store enzalutamide capsules between 20°C to 25°C (68°F to 77°F) in a dry place and keep the container tightly closed. Excursions permitted from 15°C to 30°C (59°F to 86°F). The expiration date for each lot utilized in this study will be obtained from commercial packaging.

Stability studies have been completed after 24 hours for the liquid enzalutamide after it has been extracted from the capsule. The concentration of enzalutamide extracted from the capsule at time 0 was compared to the concentration of enzalutamide at 24 hours post extraction. During the 24 hour period, liquid enzalutamide was stored in Baxter EXACTAMED oral 10mL amber syringes. The enzalutamide concentration at 24 hours post extraction decreased by 3.04% indicating stability at this time point (a concentration +/- 10% from time 0 was concerned acceptable). Additional stability studies are ongoing.

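### Section 8.2 sets the equivalence limits at -40 to 0 ug*h/mL, so identical formulations lie on the non-equivalence boundary, and section 8.4.2 contains no equivalence rule at all

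*Combined protocol and SAP*

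**What the plan says.** The primary objective (1.1.1) is: "To evaluate the bioequivalence of two oral formulations of enzalutamide following a single 160 mg dose". Three places bear on how that question is to be answered.

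- **8.2, criterion in words.** A fall of about 30-40 ug*h/mL in AUC is tolerable, glossed as "less than a 20% decrease in the AUC for the test version vs. the standard formulation". The expected fall is about 10%, put at roughly 20 ug*h/mL.
- **8.2, hypotheses.** Power of 80% is claimed with 6 patients per sequence, against two nulls of non-equivalence. The lower one is worded "the Arm B mean minus the Arm A mean is below -40"; for the upper one the text has "the null hypothesis that the Arm B mean minus the Arm A mean is above 0" (both limits in ug*h/mL). The assumed true difference is -20, the SD of differences is 20, and "each test is made at the 5% level". The accrual ceiling is 14.
- **8.4.1 and 8.4.2, analysis.** AUC for the two administrations is compared and "the difference assessed for statistical significance at the 0.05 level using the non-parametric procedures" of a cited 1972 paper on two-period crossover designs. No equivalence limits, one-sided tests or confidence interval are mentioned.

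**The concern.** The two nulls in 8.2 leave -40 to 0 as the equivalence region. Zero is its upper edge, so rejecting the second null means showing, at one-sided 5%, that the liquid gives **lower** exposure than the capsule. A product with the same exposure should fail, and one with slightly higher exposure should fail more often. That does not fit the paragraph's own criterion, which sets a maximum decrease and does not require one.

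The analysis section then tests a different hypothesis. A significance test of the difference cannot establish equivalence: a non-significant result is not evidence of similarity, and a significant one says nothing about whether the difference is small enough. The hypotheses powered in 8.2 are not those analysed in 8.4.2, and neither set properly answers the primary question.

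**Working it through.** **Inputs, all from 8.2:** limits -40 and 0; true difference -20; SD of within-patient differences 20; n = 12 (6 per sequence); one-sided 5% for each test.

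**Method.** Two one-sided t-tests on the crossover difference, with df = n - 2 = 10. Power is exact, integrating over the chi-square distribution of the estimated variance.

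- SE = 20/√12 = 5.774
- t(0.95, 10) = 1.812, so the half-width at SD 20 is 1.812 × 5.774 = 10.46
- To pass, the observed mean difference must lie between -40 + 10.46 = **-29.5** and 0 - 10.46 = **-10.5**

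An observed difference of zero is outside that window.

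**Reproducing the plan's figure.** At -20, power is 78.4% with n = 10 and 88.4% with n = 12. Twelve is thus the smallest balanced size reaching 80%; the 80% is a design target and not an arithmetic error. With limits of ±40 the smallest balanced size would have been 8 (80.2%). The sample size is therefore consistent with limits of -40 to 0 having been used, which makes a typing slip unlikely.

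**Chance of concluding equivalence under the 8.2 limits (n = 12, SD 20):**

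| True difference (liquid - capsule) | Probability |
|---|---|
| -20 | 88.4% |
| -10 | 48.7% |
| -6 | 25.0% |
| -5 | 20.1% |
| 0 | 5.0% |
| +5 | 0.7% |

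At a true difference of zero, the probability cannot exceed the 5% level of the upper test. It is 5.0% at n = 12, 50 and 200 with SD 20, and at n = 12 it is 4.7% with SD 30 and 2.7% with SD 40.

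**What 8.4.2 would do.** Taking a two-sided 0.05 t-test as a parametric stand-in for the rank procedure, a significant difference is found 87.6% of the time at the plan's own expected -20 (n = 12, SD 20). The plan does not say what that result would mean for bioequivalence.

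**Limits with zero inside (n = 12).** The ±30 and ±40 limits mirror the 30-40 in 8.2. SD 30, the ratio limits and the CVs are assumptions, because the documents do not give them.

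| Limits | Variability | Power at expected decline | Power at no difference | Smallest even n for 80% at expected decline |
|---|---|---|---|---|
| ±40 | SD 20 | 94.2% at -20 | over 99% | 8 |
| ±40 | SD 30 | 69.3% at -20 | not shown | 16 |
| ±30 | SD 20 | 48.8% at -20 | 99.8% | 28 |
| Ratio 0.80-1.25 | CV 7% | 98.4% at 0.90 | over 99% | not shown |
| Ratio 0.80-1.25 | CV 10% | 85.2% at 0.90 | over 99% | not shown |
| Ratio 0.80-1.25 | CV 15% | 56.2% at 0.90 | 92.1% | 22 |

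The CV of 7% corresponds to the plan's SD: (20/√2)/200 = 7.07%, where 200 is the mean AUC implied by equating 10% with about 20. At CV 15% and a ratio of 0.95, power is 83.1%.

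**The case against.** **The 8.2 figures describe a test that 8.4.2 does not plan.** This is true. If 8.4.2 governs, the 5% result never arises. But the primary question is then addressed only by a test of difference, which has no equivalence rule. The two sections fail in different ways, and neither rescues the other.

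**The wording could literally mean a decrease of between 0 and 20%, which is exactly -40 to 0.** That is the most charitable reading and may be how the limits arose. It still classes identical exposure, and any increase, as not equivalent. If only the question of not more than 20% lower was intended, the upper null should not be there.

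**A decline near -20 may be realistic.** Sections 3.2 and 10.1.5 acknowledge drug left in the syringe, and 10.1.3.2 describes needle extraction from cut capsules. The 3.04% concentration loss over 24 hours in 10.1.4 is a storage result, not an AUC difference. This stands: the documents do not establish the true difference. The finding does not need them to, because limits must behave sensibly at zero whatever difference is expected.

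**The sample-size consequences depend on the AUC scale.** This also stands. Equating 10% with 20 implies a mean AUC near 200. Section 1.2.2 quotes 185 for fasted capsule AUC over days 1-7, but AUCinf of 237 and 292. A 10% decline from the latter two is 23.7 and 29.2, where ±40 at SD 20 and n = 12 gives 84% and 54% power.

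**This is a pilot, and section 10 says it is not meant to support a significant labelling change.** That may excuse imprecision. It does not excuse the lack of a coherent rule for the sole primary objective.

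**Conclusion.** The concern holds and must be fixed. Under 8.2, identical formulations would be declared equivalent at most 5% of the time at any sample size or SD. The stated 80% power applies at -20 and does not describe what the trial could conclude near zero, where the probability falls to 49% at -10 and 5% at 0. Under 8.4.2, equivalence is never tested.

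The placement of zero on a null boundary and the absence of limits from 8.4.2 are matters of text and need no assumption. The probabilities rest on normally distributed differences, SD 20 and 12 evaluable patients; a rank-based analysis would shift them somewhat. Whether n = 12 suffices after correction is conditional on the limits, the variability and the AUC scale.

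**What to change.** 1. **8.2:** replace the limits with a pair that has zero in the interior, written as Treatment B minus Treatment A (liquid minus capsule), since 2.3.1 uses the arm letters for sequences. Examples are a geometric mean ratio of 0.80 to 1.25, or -40 to +40. The documents give the lower limit only as 30-40 and name no upper limit above zero, so the sponsor must choose and justify both, stating the AUC scale to which any absolute limits refer.
2. **8.4.1 and 8.4.2:** carry the same limits forward as the decision rule, in place of the test of difference. Conclude equivalence only if the 90% confidence interval for the treatment difference or ratio lies wholly within the limits. A non-parametric interval from the same crossover approach is acceptable.
3. **Power:** restate it for the chosen limits at plausible true values (0, -10, -20, or ratios 1.00, 0.95, 0.90) and a range of SDs, and say whether 12 patients still give 80%.

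**Cost.** Text changes in three sections and a new power statement, with no change to visits or sampling. At the plan's -20, or a ratio of 0.90, 12 patients are enough for ±40 at SD 20, or for 0.80-1.25 at a CV up to about 10%. They are not enough for ±30 at SD 20 (28 needed), ±40 at SD 30 (16) or 0.80-1.25 at CV 15% (22), all above the ceiling of 14. The downside is that a modestly higher exposure with the liquid would also count as equivalent.
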